Investigating the effects of a spinal mobilisation intervention in people with lower back pain.

NCT number: 04012970

Date: 27/06/2016

Study Protocol

Participants

40 participants were recruited for this study via posters, social media and word of mouth. If interest in the study was shown, an information sheet with inclusion and exclusion criteria was given to the participant. If inclusion and exclusion criteria were met, the participant was randomly sorted into a group by a random group generator and testing sessions for the intervention and control were arranged.

Procedure

Participants were involved in both a control and a spinal mobilisation intervention session. All participants were informed about details of the study and provided written consent to take part. All data collection took place in the same treatment room at the Edinburgh Napier Sighthill campus, on the same standard physiotherapy plinth. Both sessions were arranged as close to the same time of day as possible to avoid additional environmental influences. Ambient room temperature was controlled (between 20° and 23° Celsius) for all sessions. All participants completed the Oswestry Disability Index (ODI) questionnaire and an ODI scoring sheet prior to their first session to categorise their level of lower back pain. Anthropometric measures for height, mass, waist circumference and gender were also taken.

Outcome measures for muscle stiffness, tone and elasticity were taken immediately before and after both sessions. The pre intervention stiffness measure determined which side the therapy was applied to. This was based on the greatest mean value for stiffness following 3 recorded measures, therefore working on the stiffer side of the spine. The location for measurements was identified on both sides of the spine on erector spinae (longissimus). Measurements were taken from the central belly of this muscle by asking the participant to lift their head and feet at the same time contracting their back muscles. This spot was marked to ensure pre and post measures were taken at the same location. The distance and width from the base of the spine was measured to locate the same spot for their 2nd session.

The intervention was conducted by a physiotherapist with extensive experience in spinal mobilisation therapy. The intervention involved mobilisations on the lumbar spine (L1 to L5) for 30 minutes on the determined side of the participant lying prone. The control session involved no physical touch. The participant lay either prone or supine on the same plinth and encouraged to relax for 30 minutes.

Outcome measures

Measurements for para-spinal muscle stiffness, tone and elasticity were taken using a myometer palpation device (MyotonPRO). This previously validated handheld device has been documented to give reliable results for muscle stiffness, tone and elasticity. The myometer uses a series of low force mechanical impulses registered as an oscillation in the form of an acceleration signal. The stiffness, tone and elasticity parameters are reported as a mean of these impulses along with the coefficient of variation (CV). Values were only accepted if the CV was <3%, complying with the manufacturer recommendations.

Statistical Analysis Plan

Participant data was stored on password protected excel files on University computers. All participant names were replaced with a pseudonym and therefore participant data was not identifiable. Summary data was then used for statistical analysis.

Analysis was carried out on each dependent variable (muscle stiffness, tone and elasticity) in separate 2-way repeated measure within participant ANOVAs. This was to determine any significant differences occurring due to the independent variables (condition and time). Covariates were also assessed in separate ANCOVAs to determine any significant factors contributing to their changes. All statistical analysis was out using SPSS 23 with the alpha level set at 0.05.

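### The randomised group is undefined; if it means session order, the planned ANOVA leaves it out, at a cost in power that is small unless the session effect is large

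*Combined protocol and SAP*

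**What the plan says.** The Participants section states that "the participant was randomly sorted into a group by a random group generator" and, in the same sentence, that "testing sessions for the intervention and control were arranged". It does not say what the groups are, how many there are, or in what ratio they were formed. The Procedure section then says: "Participants were involved in both a control and a spinal mobilisation intervention session". It mentions a first and a second session, but not which condition came first or how far apart the sessions were.

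The Statistical Analysis Plan analyses each outcome "in separate 2-way repeated measure within participant ANOVAs", with condition and time as the only independent variables. It adds: "Covariates were also assessed in separate ANCOVAs to determine any significant factors contributing to their changes". Those covariates are not named. No group, order or session term appears anywhere in the plan.

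**The concern.** Since everyone receives both conditions, the randomisation cannot have allocated treatment. The sentence moves straight from random sorting to arranging the two sessions, so the most natural reading is that it allocated session order. The documents never say so.

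On that reading the design is a two-period crossover whose randomised factor is missing from the model. Suppose the pre-to-post change in muscle stiffness, tone or elasticity tends to differ between a first and a second visit. Participants who had mobilisation first and those who had it second then differ systematically in the intervention-minus-control contrast, and a model without order treats that difference as noise. Two things are at stake: power and, if the orders are clearly unequal in size, an estimate shifted for that particular split.

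A session shift that moves the pre and post values equally cancels from condition-by-time and causes neither problem.

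**Working it through.** **Inputs from the documents.** There are 40 participants (Participants section), two sessions each, with outcomes before and after each session (Procedure). The model factors are condition and time, with alpha 0.05 (Statistical Analysis Plan). There is no sample-size calculation, so there is no figure to reproduce.

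**Assumptions.** The test is two-sided, there is no dropout, and condition-by-time is the effect that tests the intervention. The effect is τ = 0.454 SD of the paired contrast, chosen because it gives 80% power at n = 40 with no session effect. The session effect π is the first-minus-second session difference in change, in the same SD units, and is varied from 0 to 1.0. The split is not stated, so fixed splits and simple 1:1 randomisation are both shown.

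**Step 1: reduce the test.** For each participant let D = change in the intervention session minus change in the control session. The condition-by-time test is a one-sample t test on D with 39 df.

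**Step 2: model.** D = τ + sπ + e, with s = +1 if the intervention came first and −1 if second, and e ~ N(0, 1). Let n1 and n2 be the numbers in the two orders.

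**Step 3: planned analysis, no order term.**
- The mean of D is N(τ + π(n1 − n2)/40, 1/40).
- The sum of squares is noncentral chi-square with 39 df and noncentrality π²(40 − (n1 − n2)²/40).
- The critical t is 2.0227.
- Example at 20:20, π = 0.5: noncentrality 0.25 × 40 = 10, so the expected error variance is (39 + 10)/39 = 1.26 instead of 1.
- Example of the shift at 25:15, π = 0.5: 0.5 × 10/40 = 0.125 SD.

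**Step 4: with order as a factor.** Take the equally weighted mean of the two order means. Its variance is 0.25(1/n1 + 1/n2), on 38 df, with critical t 2.0244. At 20:20 the variance is 0.25 × (1/20 + 1/20) = 0.025 = 1/40, the same as without the term. At 25:15 it is 0.25 × (1/25 + 1/15) = 0.0267, about 7% more.

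**Step 5: power (%), by numerical integration.**

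| π (SD) | 20:20, no order term | Averaged over simple 1:1, no order term |
|---|---|---|
| 0 | 79.96 | 79.96 |
| 0.1 | 79.67 | 79.56 |
| 0.25 | 78.14 | 77.53 |
| 0.454 | 73.88 | 72.21 |
| 0.5 | 72.56 | 70.67 |
| 1.0 | 50.25 | 50.45 |
| **With order term, any π** | **79.90** | **78.86** |

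Simulation with 400,000 replicates per scenario agrees: at 20:20 and π = 0.5, 72.6% without the term and 80.0% with it.

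**Step 6: break-even.** At 20:20 the order term costs only one degree of freedom (79.96% to 79.90%), and the powers cross at π = 0.043. If τ is instead set to give 30% to 90% power, the crossing lies between 0.031 and 0.046. Under simple randomisation the adjusted test also pays for chance imbalance (78.86% on average), and the crossing moves to π = 0.168. The fourfold difference comes from the allocation assumption alone.

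**Step 7: type I error (%) of the planned test.**

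| Split | π = 0.25 | π = 0.5 | π = 1.0 |
|---|---|---|---|
| 20:20 | – | 2.9 | 0.6 |
| 23:17 | 4.9 | 4.7 | 3.4 |
| 24:16 | – | 6.2 | 6.5 |
| 25:15 | 6.0 | 8.2 | 11.7 |

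(A dash marks a value not computed.) Under simple randomisation 73.2% of allocations are 23:17 or closer and 15.4% are 25:15 or worse. Averaged over all of them, type I error is 5.0% at every π.

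**The case against.** The strongest reply is that the point needs two things that the documents do not establish: that group means session order, and that the change differs between sessions. On the second, the Procedure reduces the scope for a session effect: the room, plinth and measurement spot were kept the same, the time of day was matched as closely as possible, and room temperature was controlled. Even granting both, the averaged type I error is 5%, and at 20:20 the planned test is conservative. At π = 0.25 the order term gains only 79.90 − 78.14 = 1.8 points at 20:20, or 78.86 − 77.53 = 1.3 points on average. The large losses need a session effect of 0.5 or 1.0 SD, which is 1.1 or 2.2 times the assumed treatment effect. With no session effect, adding the term slightly reduces power. All of this stands, and it keeps the point minor.

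It might also be said that the separate ANCOVAs could include order. That cannot be ruled out, but with the covariates unnamed nothing shows that they do.

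A reader might infer from the missing order term that the planned test is invalid or its estimate biased. The documents do not support that: bias and type I inflation arise only conditionally on a clearly unequal split, and the split is not reported. Nor do they support a single threshold such as 0.17 SD for when the term is worth having. That value belongs to simple randomisation; a random group generator may equally force equal groups, in which case the value is about 0.04.

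**Conclusion.** The point holds as a minor efficiency matter joined to a real gap in description. The only randomised feature of the study is undefined, is most naturally session order, and is in no stated model. If it is order, and if the change differs between sessions, leaving it out costs about 2 points of power at 0.25 SD, 7 points at 0.5 SD and 30 points at 1.0 SD at a 20:20 split. It also shifts the estimate by π(n1 − n2)/40 when the orders are unequal.

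These sizes rest on 40 analysed participants and an assumed effect of 0.454 SD. The documents give no power target, outcome SD, split or evidence of a session effect, so they do not show that any power was actually lost. Confidence is medium, mainly because the meaning of group is inferred.

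**What to change.** State what group means and report the number of participants in each session order. If group is session order and was recorded, add order as a between-participant factor to each of the three repeated-measures ANOVAs, and test condition-by-time as the equally weighted average over the two orders (the Type III test). If order was not recorded, or was the same for everyone, say so as a limitation. The order term does not correct for carry-over between sessions, and the report should not suggest that it does.

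The documents are written in the past tense, so the modelling part means a re-analysis as well as new wording in the Statistical Analysis Plan. It uses one degree of freedom. With no session effect it lowers power by about 0.1 point at 20:20, about 1 point on average under simple randomisation (79.96% to 78.86%), and about 3 points at 25:15 (80.0% to 77.3%). Defining group and reporting the counts needs wording only, provided the records exist.

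### No minimum interval between the two sessions and no order or period term: carry-over from mobilisation would dilute the condition main effect, while the condition-by-time interaction is largely protected

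*Combined protocol and SAP*

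**What the plan says.** The design is within-participant: "Participants were involved in both a control and a spinal mobilisation intervention session" (Study Protocol, Procedure). Under Participants, "the participant was randomly sorted into a group by a random group generator and testing sessions for the intervention and control were arranged". The text does not say that the group is the session order, and it gives no allocation ratio.

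On timing, Procedure has one rule: "Both sessions were arranged as close to the same time of day as possible to avoid additional environmental influences". No minimum, target or maximum interval is given. A separate visit is implied by "The distance and width from the base of the spine was measured to locate the same spot for their 2nd session".

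On measurement, "Outcome measures for muscle stiffness, tone and elasticity were taken immediately before and after both sessions". The side to be treated is the one with the higher mean stiffness before the intervention. The comparator is 30 minutes of lying at rest, and "The control session involved no physical touch".

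The Statistical Analysis Plan runs a two-way within-participant ANOVA for each outcome. Its stated purpose is: "This was to determine any significant differences occurring due to the independent variables (condition and time"). It lists no order, period or carry-over term, does not say which ANOVA effect carries the treatment conclusion, and does not name the ANCOVA covariates.

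**The concern.** The plan as written allows one participant's control session to fall the day after mobilisation and another's to fall weeks after it. The control involves no touch, so any treatment residual runs one way, from mobilisation into a later control session. Balancing the order limits the contamination to the participants mobilised first, but nothing in the other order offsets it.

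The effect tested matters. The condition main effect averages the pre and post readings of each session, so it includes readings taken before any treatment and absorbs the whole residual. A small or null condition main effect could mean that mobilisation did little, or that its effect was still present at the control session. The planned model could not tell these apart, because it never compares the two orders.

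**Working it through.** **Inputs from the documents.** "40 participants were recruited for this study via posters, social media and word of mouth". Each participant has two sessions with a pre and a post reading at each. The factors are condition and time. The documents give no power calculation, effect size, SD or interval, so there is no stated figure to reproduce.

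**Assumptions.** τ is the true change produced by mobilisation, with rest producing none. A share s of participants is mobilised first (s = 0.5 unless stated). A fraction c of τ is present at the start of their control session. The documents give no value for c or s.

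**Condition main effect, residual constant over the control session.**
- Mobilisation session mean: (0 + τ)/2 = τ/2.
- Control session mean: s·c·τ = cτ/2.
- Difference: τ/2 − cτ/2 = (1 − c)·τ/2.
- For c = 0.25 this is 0.375τ, or 75% of the true 0.50τ. For c = 0.5 it is 0.25τ, or 50%.
- For general s the fraction kept is 1 − 2sc. At c = 0.5 that is 75% for s = 0.25 and 25% for s = 0.75.

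**Condition-by-time interaction (difference in pre-to-post change).**
- Constant residual: τ − (cτ/2 − cτ/2) = τ. No bias.
- Residual fades to zero during the rest: τ − (0 − cτ/2) = τ(1 + c/2). This is 1.125τ at c = 0.25 and 1.25τ at c = 0.5, an overstatement of 12.5% or 25%.
- For general s the fading case gives τ(1 + sc).

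Neither case shrinks the interaction.

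**What a carry-over estimate from existing readings could show.** Take session-2 minus session-1 pre-session readings and compare the two orders. Assume 20 per order and a between-session correlation r. The 95% CI half-width in SD units is t(38) × √(2(1 − r)) × √(1/20 + 1/20), with t(38) = 2.024:
- r = 0.7: 2.024 × 0.775 × 0.316 = 0.50
- r = 0.8: 2.024 × 0.632 × 0.316 = 0.40
- r = 0.9: 2.024 × 0.447 × 0.316 = 0.29

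As a test, 80% power needs a difference of about 0.89 SDs of the session-to-session change. On the scale of a single reading that is 0.89 × √(2 × 0.1) = 0.40 SD at r = 0.9, and 0.89 × √(2 × 0.3) = 0.69 SD at r = 0.7.

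**Which side to use.** Suppose the treated side is picked on the mobilisation session's own pre-reading, which is the natural but unconfirmed reading. It is then selected for being high at session 1 in one order and at session 2 in the other. Let q be the between-side correlation, with independent noise for each side at each session and no carry-over.
- The selected side is expected to fall from the selecting session to the other by (1 − r)/√(π(1 − q)).
- The fall runs in opposite directions in the two orders, so the false difference is 2(1 − r)/√(π(1 − q)).
- r = 0.9, q = 0.7: 0.2/√(0.3π) = 0.21 SD.
- r = 0.9, q = 0.9: 0.2/√(0.1π) = 0.36 SD.
- r = 0.7, q = 0.7: 0.6/√(0.3π) = 0.62 SD.

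A false signal of about 0.2 to 0.6 SD is of the same order as the precision of the check. If the side that was stiffer at session 1 is used in both orders, the same fall occurs in both and the false difference is zero. A simulation under these assumptions agreed with both results. Noise shared by the two sides within a session would make the false signal smaller.

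**The case against.** **Separate days.** Matching the time of day and relocating the measurement spot suggest that the sessions were on different days, and nothing in the documents indicates that an effect of one mobilisation session lasts that long. This stands as a limit on likelihood. It does not supply a minimum interval, a rationale for one, or a common gap across participants.

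**The pre/post design already protects the treatment contrast.** This largely stands. A reader might infer that any null or small treatment result is uninterpretable. The algebra does not support that: the raw interaction is unbiased or overstated, and the ambiguity belongs to the condition main effect. The point survives because the SAP names condition as a tested factor and does not say that inference rests on the interaction. A reader might also infer that a baseline-adjusted contrast would be understated, but the SAP specifies no such analysis.

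**The data are not ignored.** A reader might infer that nothing is measured after the immediate post reading, or that the session-2 pre-readings go unused. Neither is right. Participants mobilised first are measured again at session 2, and those readings enter the ANOVA as a level of time. What is missing is a comparison of them by order.

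**A carry-over check is weak and can mislead.** Both parts stand. The check is therefore worth reporting only as an interval estimate, on a side chosen in the same way in both orders.

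**Conclusion.** The point holds in a limited form. The documents set no minimum interval and plan no analysis by order or period, so a condition main effect would take any carry-over in full. With half mobilised first and a residual that persists through the control session, it keeps (1 − c) of its value. The raw interaction is unbiased under a constant residual and overstated by c/2 under one that fades.

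These sizes are illustrations. They rest on the group being session order, on an assumed even split, and on a c that the documents do not give. A reader might infer that the control sessions were in fact contaminated; nothing in the documents shows that. This should be changed because the remedy is cheap, but it does not by itself invalidate the trial.

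**What to change.** 1. State that the treatment conclusion rests on the condition-by-time interaction, and draw none from the condition main effect.
2. Define the groups as session orders, if that is what they are, and include order and period in the analysis. These terms allow for drift between visits and show the results by order. They do not remove carry-over.
3. Apply one common minimum interval to both orders, fixed in advance, and record actual intervals. The document is written in the past tense; if data collection is complete, report the actual intervals by order instead.
4. For each outcome, compare session-2 minus session-1 pre-session readings between orders, using in both orders the side that was stiffer at session 1 and not the treated side. Report the difference with its 95% CI as a description, not as a pre-test that decides the analysis. This needs readings from both sides at both sessions. With about 20 per order it cannot rule out a small carry-over.
5. Report the session-1-only comparison of mobilisation with control as a sensitivity analysis.

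The cost is slightly less flexible booking if sessions are still to be run, and a few short analyses. Items 1, 2 and 5 use readings already planned, and item 4 does too where both sides were recorded. The estimates in items 4 and 5 will be imprecise and should be presented as such.

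### The treated side is picked on the pre-session stiffness reading, but the SAP names neither the analysed side nor a control-session side, so regression to the mean can pass for a treatment effect

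*Combined protocol and SAP*

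**What the plan says.** Study Protocol, Procedure, on the choice of side: "The pre intervention stiffness measure determined which side the therapy was applied to". The statistic used is the larger of the two sides' means: "This was based on the greatest mean value for stiffness following 3 recorded measures, therefore working on the stiffer side of the spine".

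On timing: "Outcome measures for muscle stiffness, tone and elasticity were taken immediately before and after both sessions". Measurement sites are located on both sides of the spine, and "This spot was marked to ensure pre and post measures were taken at the same location". Distances from the base of the spine are recorded so that the spot can be found again at the second session. No reading is described that serves only to choose the side.

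Mobilisation is applied to the chosen side only. For the comparison session, "The control session involved no physical touch", and no side is assigned to it.

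The Statistical Analysis Plan says "Summary data was then used for statistical analysis", without defining the summary. Each outcome goes into a two-way within-participant ANOVA, whose purpose is given as: "This was to determine any significant differences occurring due to the independent variables (condition and time". Side is not a factor, and the interaction is not named as the efficacy test.

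**The concern.** When the larger of two error-prone means is selected, the selected value tends to carry positive error. The post-session reading on that side has fresh error with no such tilt, so stiffness is expected to fall even if mobilisation does nothing. Averaging three readings and marking the spot reduce the error but do not remove it. The 3% limit on the coefficient of variation applies to impulses within a reading and says nothing about error from pre to post.

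A control session can cancel this artefact, but only if its side is chosen in a way that carries the same bias. As no rule is given, the plan does not establish that its main contrast is valid. Time is also a listed factor, so a fall in stiffness could be reported as benefit through the time effect alone. Tone and elasticity are affected only as far as their errors correlate with stiffness error, which cannot be quantified here.

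**Working it through.** **Inputs.** From the documents: n = 40, each attending both sessions; alpha 0.05 (two-sided assumed); side chosen by the larger pre-session mean of three. Not in the documents, so assumed over a range: *s*, the within-session error SD of a mean of three, independent between sides and between pre and post; and *tau*, the SD of the true left-right difference. The plan states no effect size or SD, so there is no figure of its own to reproduce.

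**Bias of the selected pre-value.**

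b = s × √(2/π) / √((tau/s)² + 2)

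At tau = 0: 0.798/1.414 = 0.56s. At tau = 2s: 0.798/2.449 = 0.33s. At tau = 10s: 0.798/10.10 = 0.08s.

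**Four possible side rules.**
- **A.** Control is analysed on the side chosen in the mobilisation session. The bias enters one session only, so condition × time is biased towards mobilisation.
- **B.** The control side is chosen by the control session's own pre-reading. The bias cancels in condition × time but adds up in the time effect.
- **C.** Both sides are averaged in both sessions. There is no bias, but a one-sided effect is diluted.
- **D.** The side is fixed at the first session, with order balanced 20/20 (assumed). Condition × time is valid and the time effect is biased.

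**Worked case, A at tau = 0.** The selected pre-reading's error has variance s² − b², so the between-session difference in change has variance 4s² − b² = (4 − 0.318)s² = 3.682s², an SD of 1.919s. The noncentrality is 0.564 × √40 / 1.919 = 1.86. Against a critical t of 2.02 on 39 df this gives 44% rejection.

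**Worked case, B, time effect at tau = 0.** 2 × 0.564 × √40 / √(2 × (2 − 0.318)) = 3.89, giving 97%.

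**False-positive rates with no true effect.** Simulation, 6,000 trials per scenario, no session-to-session variation:

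| tau | b | A: condition × time | B: time | Mobilisation pre-post alone (A or B) | D: time |
|---|---|---|---|---|---|
| 0 | 0.56s | 44% | 97% | 77% | 44% |
| s | 0.46s | 31% | 85% | 57% | 31% |
| 2s | 0.33s | 17% | 54% | 31% | 17% |
| 3s | 0.24s | 11% | 32% | 18% | 11% |
| 5s | 0.15s | 8% | 16% | 11% | 8% |
| 10s | 0.08s | 6% | 8% | 7% | 6% |

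Condition × time stays at about 5% under B and 4–5% under D. Under C every test stays at 4–6%. If control were instead the mean of both sides while the treated side alone is used for mobilisation, condition × time rejects in 57%, 40%, 22%, 14% and 10% of trials for tau = 0, s, 2s, 3s and 4s.

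**Sensitivity to session variation.** With side-specific session variation of SD s, A condition × time becomes 24%, 20%, 14%, 12%, 7%, 5%, and B time 72%, 65%, 43%, 29%, 15%, 8%, in the row order of the table.

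**Does baseline adjustment rescue A?** It does when session variation is absent or side-specific: 4.4–5.4% in all 12 such scenarios. It does not when the variation is common to both sides: 18%, 13%, 10%, 7%, 6%, 5% (session SD = s) and 32%, 23%, 14%, 10%, 7%, 5% (session SD = 2s). Adjustment alone is therefore not a dependable remedy.

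**The case against.** The strongest reply is that the documents show a reporting gap and not a demonstrated bias. The summary data may be the average of both sides, in which case nothing is biased. Under B and D the condition × time test keeps its level, and a two-way ANOVA ordinarily yields that test. The largest rates, 97% and 77%, belong to tests that do not compare mobilisation with control, and the SAP does not list the second at all. Neither *s* nor *tau* is known; the tau = 0 row assumes that nobody has a true left-right difference, and from tau = 5s upward the rate under A is 8% or less.

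Much of this stands. The size is unknown and the consequence depends on the side rule. But that rule is exactly what is missing, and it decides whether the main contrast is valid. Relocating the same spot at the second session does not settle the side, since spots on both sides could be relocated, but it fits A, the harmful case, at least as well as the others. Reporting the time effect as benefit would be a misuse, yet the SAP lists time as a factor and does nothing to rule this out.

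There is also a fair point about the remedy. Choosing a control side afresh sits awkwardly with the intention to return to the same spot, and it compares opposite sides in some participants.

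**Conclusion.** The concern holds. If the treated side is analysed and there is any measurement error, part of its pre-post fall is an artefact. Whether the artefact reaches the between-condition test depends on a control-side rule that the plan does not give. If control uses the same anatomical side, it does, and the false-positive rate can be anything from close to nominal to several times nominal. If control follows its own pre-reading, or the side is fixed at the first session with balanced order, the damage is confined to the time effect and, under the former rule, also to within-session change in each session. If both sides are averaged, there is none.

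The conclusion rests on the inference that the treated side was analysed, on independent errors before and after, and on assumed ranges for *s* and *tau*. The bias is small when true left-right differences are large relative to error. This should be fixed. Confidence is medium, because the size cannot be pinned down from the documents.

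**What to change.** Leave the rule for choosing the therapy side as it is. In the SAP:

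1. Name the side that is analysed.
2. Set an index side in the control session by the identical rule, from that session's own pre-readings, and analyse only the index side in each session.
3. Draw the efficacy conclusion only from the between-condition contrast: condition × time, or post values adjusted for pre values under this symmetric rule.
4. State that the time main effect and within-session change are not evidence of efficacy.
5. Report the average of both sides as an unbiased but diluted sensitivity analysis.

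Under the symmetric rule both contrasts in step 3 held 4.5–5.7% in all 24 scenarios (six values of tau by four session-variation settings). For an assumed purely one-sided effect of 1.0s, condition × time power was 87–92%, against 58–60% with both sides averaged. At tau = 0 with no session variation, the noncentralities are √40 / √(2 × (2 − 0.318)) = 3.45 and 0.5 × √40 / √2 = 2.24.

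**Cost.** Wording and re-analysis, as the study is described in the past tense. The index side will differ between a participant's two sessions with probability arccos(tau²/(tau² + 2s²))/π, which is 50%, 39%, 27%, 19%, 12% and 6% for tau = 0, s, 2s, 3s, 5s and 10s; the power figures already include this. The fix needs both-side readings from the control session. The documents say sites were located on both sides, not that both were read each time. If they were not, this should be reported as a limitation. A separate selection reading would also restore about 5%, but only in a future study.

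### Mobilisation is given prone, but the control rest may be prone or supine, so body position is partly confounded with condition

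*Combined protocol and SAP*

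**What the plan says.** Under Study Protocol, Procedure, each participant attends two sessions: "Participants were involved in both a control and a spinal mobilisation intervention session". The two are described as follows.

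- **Intervention:** "The intervention involved mobilisations on the lumbar spine (L1 to L5) for 30 minutes on the determined side of the participant lying prone". No other position is mentioned.
- **Control:** "The control session involved no physical touch", and "The participant lay either prone or supine on the same plinth and encouraged to relax for 30 minutes".

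The timing of the readings is also given there: "Outcome measures for muscle stiffness, tone and elasticity were taken immediately before and after both sessions".

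The Statistical Analysis Plan puts each outcome into its own two-way repeated-measures ANOVA with condition and time as the factors. It then adds: "Covariates were also assessed in separate ANCOVAs to determine any significant factors contributing to their changes". Those covariates are not named.

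The documents do not say who decided the control position, whether it was recorded, or how many participants lay supine.

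**The concern.** The control is defined by the absence of touch, so touch is the difference the study means to isolate. For a participant who rested supine, the two sessions also differ in body position. That participant's contrast compares prone lying with mobilisation against supine rest. For a participant who rested prone, the contrast is matched on position. The trial averages the two kinds in unknown proportions.

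The outcomes are stiffness, tone and elasticity of the para-spinal muscles. Lying supine places the back against the plinth and lying prone leaves it free, so an effect of position on these readings cannot be dismissed in advance, though the documents do not show that one exists. If it does exist, a significant result could be partly positional, or a real mobilisation effect could be hidden. The protocol holds room, plinth and temperature constant and keeps time of day as close as possible. It leaves position free in one condition only and gives no reason.

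**Working it through.** The plan gives no effect size, SD or power statement, so there is no figure of its own to reproduce. The check has two parts: a reading of the design, and an illustration of scale under assumed values.

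**1. Does anything in the plan remove the difference?**

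- *Within-participant comparison.* It cancels stable traits. Position can differ between one person's two sessions, so it does not cancel.
- *Pre-session reading.* It cancels baseline differences. Position acts between the pre and post readings, so its effect enters the change score.
- *Randomisation.* However participants are allocated, supine lying can occur only in a control session.
- *Model.* The ANOVA factors are condition and time. Position is not named as a factor or a covariate.

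**2. What does the contrast estimate?**

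With two conditions and two time points, the condition-by-time F test equals a two-sided paired t test on (intervention change − control change). Let

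- m = mobilisation effect relative to prone rest,
- d = change under prone rest minus change under supine rest,
- q = share of participants supine in the control session.

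If the effects add, the expected contrast is m + q·d. The bias is q·d, which is zero when q = 0 or d = 0.

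**3. How large could it be?**

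Inputs:

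- n = 40, the number recruited (Participants section); all are assumed to be analysed.
- Alpha = 0.05 (Statistical Analysis Plan).
- q and d are assumed. d is in SDs of the paired contrast, with that SD set to 1 apart from the mixture of positions.
- One value per participant, with the condition-by-time interaction taken as the key test.

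The standardised mean is (m + q·d) / √(1 + q(1 − q)d²). The rejection rate comes from the noncentral t with 39 df and noncentrality √40 times that value.

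Example: for m = 0, q = 0.5, d = 0.5, this is 0.25 / √(1 + 0.25 × 0.25) = 0.25 / 1.031 = 0.243, and the rejection rate is 32.2%.

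False-positive rate with m = 0:

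| d (SD) | q = 0 | q = 0.25 | q = 0.5 | q = 0.75 |
|---|---|---|---|---|
| 0 | 5.0% | 5.0% | 5.0% | 5.0% |
| 0.1 | 5.0% | 5.3% | 6.1% | 7.5% |
| 0.25 | 5.0% | 6.7% | 11.9% | 21.0% |
| 0.5 | 5.0% | 11.7% | 32.2% | 61.8% |

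Masking, with m = 0.5 and q = 0.5 (power without bias 86.9%):

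- d = −0.25: (0.5 − 0.125) / 1.008 = 0.372, power 63.1%.
- d = −0.5: (0.5 − 0.25) / 1.031 = 0.243, power 32.2%.

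A simulation of the paired contrast with 200,000 replicates per cell agreed to within about half a point.

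**The case against.** The strongest reply is that no harm has been shown. Bias needs a material share of supine controls and a posture effect that lasts to the post reading, and the documents establish neither. This stands. The table shows how bias would scale, not that it occurred, and its most extreme cell should carry no weight in judging severity.

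Second, the measurement site was found by having participants raise head and feet to contract the back muscles. This suggests, without saying so, that readings were taken prone in both sessions. A supine control participant would then have turned over first, which might weaken any effect. This narrows the point to position during the 30 minutes rather than at the reading. It does not remove it, because the post reading follows immediately.

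Third, mobilisation as delivered against ordinary lying rest could be a legitimate pragmatic contrast, with position as part of the package. That reading is open, but the plan does not state it, and a result attributed to mobilisation itself would still need matched positions.

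Fourth, the plan does not name the interaction as the key test. It is, however, the natural test of a treatment effect in a pre/post by condition ANOVA.

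Finally, the text is in the past tense, so for sessions already run only re-analysis or a stated limitation is available. This also stands, and the fix below allows for it.

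**Conclusion.** The concern holds. Position is partly confounded with condition, and neither the design nor the planned analysis removes an effect of position that arises during the session. Neither size nor direction can be determined from the documents. The bias is nil if every control lay prone or if position does not affect these readings. The inflation is small for a weak posture effect (about 6% against a nominal 5% at 0.1 SD with half supine) and substantial for a moderate one (32% at 0.5 SD with half supine). These figures assume additive effects, all 40 participants analysed, and the condition-by-time interaction as the key test. The point should be addressed, but it does not by itself invalidate the result. Confidence is medium, because the two deciding quantities are unknown.

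**What to change.** **Further or repeat sessions.** Reconcile the two position statements so that body position is the same in both sessions. This takes one procedural line and no extra staff or visits. The small downside is that the control position is no longer flexible.

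**Completed sessions, position recorded.** Report how many controls lay supine. Repeat the condition-by-time contrast, as a sensitivity analysis, in participants whose control position matched their intervention session. No new data are needed, but precision falls. Power for a true 0.5 SD paired effect (noncentral t, n − 1 df) is:

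| Matched participants | Power |
|---|---|
| 40 | 87% |
| 30 | 75% |
| 20 | 56% |
| 10 | 29% |

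The report should say that the subset is smaller and possibly selected. Adding a posture factor is no substitute, since it can only compare different people's control sessions. Split 20 against 20, it has 34% power for 0.5 SD (noncentrality 0.5 / √(1/20 + 1/20) = 1.58, 38 df), so a non-significant posture term would not be reassuring.

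**Completed sessions, position not recorded.** State that the contrast estimates mobilisation plus any difference due to position. This costs one sentence.
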